4.2.1.2 Sensitivity analyses and supplementary analyses

The following sensitivity analyses and supplementary analyses of the primary endpoint will be performed:

Impact of estimation by means of two separate models

The impact that the choice utilizing two separate models for the total and the chronic slope has on the results of the main analysis will be evaluated following the approach described in Vonesh et al 2019. Explicitly, rather than fitting two separate models, one for the total and one for the chronic slope, a single model that assumes a piecewise linear trend in eGFR in the two treatment arms (two slopes, acute and chronic) will be fitted.

The presentation of the results will include estimates of the difference in mean chronic and total slopes (the latter obtained through a weighted combination of the chronic and the acute slope estimates, with weights corresponding to the relative durations of the slopes, see Vonesh et al 2019, Equation 3). The corresponding standard deviations, confidence intervals and p-values will also be provided.

Again, due to the early close-down of the study and the ensuing unavailability of late eGFR measurements, only measurements taken up to and including visit 17 (week 69) will be included in the mixed-effects model.

Impact of choice of acute-chronic slope separation

The impact that the different choices of the starting point of the chronic slope have on the results of the main analysis will be evaluated by means of constructing a series of two-slopes models, as described above, where the point of connection between the acute and the chronic slopes, the “knot”, will be allowed to move. The models will be compared by means of AIC.

The results for each of these models will include estimates of the difference in mean chronic and total slopes, the corresponding standard deviations, confidence intervals and p-values, as well as AIC.

Again, due to the early close-down of the study and the ensuing unavailability of late eGFR measurements, only measurements taken up to and including visit 17 (week 69) will be included in the mixed-effects model.

Impact of eGFR calculation methodology

During the course of the study, the method of calculating eGFR was changed, excluding race from the calculation. The main eGFR based analyses will be using the eGFR obtained according to the new approach. However, a sensitivity analysis, in which the main analysis of the primary endpoints will be replicated using the original eGFR calculations (i.e., where race was included), will be performed in order to evaluate the potential impact of the difference in eGFR calculation methodologies.

Again, due to the early close-down of the study and the ensuing unavailability of late eGFR measurements, only measurements taken up to and including visit 17 (week 69) will be included in the mixed-effects model.

4.2.1.3 Supplementary analyses

The following supplementary analyses of the primary endpoint will be performed:

Impact of introduction of concomitant medications

Two supplementary analyses (one for each of the primary endpoints) will be performed for the evaluation of the potential impact that the intercurrent events of an introduction of a long-term treatment that affects either potassium, or eGFR profile, will have on the treatment effect of SZC.

For the analyses, the eGFR measurements that are obtained after the introduction of long-term potassium-lowering concomitant treatment or concomitant medication that has direct effect on CKD progression will be removed. That is, the time point at which such treatments are introduced will be regarded as a point of censoring.

The main analysis of the primary endpoint will then be replicated using the resulting data set.

Again, due to the early close-down of the study and the ensuing unavailability of late eGFR measurements, only measurements taken up to and including visit 17 (week 69) will be included in the mixed-effects model.

4.2.1.4 Supportive analyses

The following supportive analyses of the primary endpoint will be performed:

Impact of subgroups

The homogeneity of effect observed in the main analysis will be examined in the following sub-groups:

- Normokalaemia yes/no, as determined by the screening potassium measurement (i.e., the stratification factor)
- Geographic Region (see Section 4.1.4.1 as well as Appendix 7.2)
- Diabetes at screening (Yes/No)
- SZC dose at randomization (5g QOD or 0, 5, 10, 15 g QD)
- RAASi dose at randomisation (guideline-directed / less than guideline-directed as per CSP Appendix B3)
- RAASi dose at screening (guideline-directed / less than guideline-directed as per CSP Appendix B3)

- Age at screening ($< 65, \geq 65$ years)
- Sex (Male, Female)
- eGFR at screening ($< 45, \geq 45$ ml/min/1.73 m 2)
- eGFR at randomisation ($< 45, \geq 45$ ml/min/1.73 m 2)
- UACR classification at screening ($<1000, \geq 1000$ mg/g)
- Systolic blood pressure classification at screening (see Section 4.1.4.1)
- CKD aetiology class at screening (see Appendix 7.1 for details)
- SGLT2 inhibitors and/or finerenone at randomisation (yes / no)

All the subgroup analyses will be performed by means of fitting two sets of mixed models. In order to obtain the effect estimates as well as the corresponding CIs for a particular subgroup, a mixed model, as described in Section 4.2.1.1, will be fitted to each sub-group separately. In order to evaluate the statistical significance of the potential difference in effect between the sub-groups, a separate model will be created. In addition to the covariates used in the main analysis, it will also include the sub-group as a factor, as well as an interaction between the sub-group factor and each of the three main covariates (treatment, time, and the interaction between the two). The homogeneity of effect will be tested by applying a likelihood ratio test corresponding to the subgroup-by-treatment interaction term.

Again, due to the early close-down of the study and the ensuing unavailability of late eGFR measurements, only measurements taken up to and including visit 17 (week 69) will be included in the mixed-effects models.

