b The participant must be confirmed normokalaemic (L-lab S-K) at the end of the run-in phase (Visit 6a) prior to randomisation. The date of randomisation is Day 1 of the maintenance phase. All assessments/procedures designated at this visit should be performed prior to randomising the subject, except for SZC/placebo and lisinopril/valsartan accountability.

c The investigator must ensure that Visits 7 and 8 occur 2 and 7 (±1) days after randomisation, respectively.

d For details regarding early treatment discontinuation, see Section 7.1.

e For details regarding ESD, see Section 7.2.

f Week refers to the end of the week, eg: Week 6 is the end of the sixth week (ie, Day 43 [6 weeks × 7 days + 1 = 43]); Week 12 is the end of the twelfth week (ie, Day 85 [12 weeks × 7 days + 1 = 85]), etc.

g Accountability refers to collection/dispensation/re-dispensation of study intervention (SZC/placebo and lisinopril/valsartan).

h Dispensation only.

i Collection only.

j The minimum local laboratory clinical chemistry tests for safety monitoring will include sodium, potassium, bicarbonate, chloride (electrolytes) and urea nitrogen and creatinine (kidney). The S-K and S-Cr samples collected and analysed by local laboratory at study visits and as part of routine clinical practice can also be used to adjust doses of SZC/placebo and lisinopril/valsartan.

AE, adverse event; BP, blood pressure; C-lab, central laboratory; CSP, clinical study protocol; ECG, electrocardiogram; ED, early discontinuation; eGFR, estimated glomerular filtration rate; FU, follow-up; IRT/RTSM, interactive response technology/randomisation and trial supply management; L-lab, local laboratory; POCBP, participants of childbearing potential; R, randomisation; SAE, serious adverse event; S-Cr, serum creatinine; S-K, serum potassium; SZC, Sodium zirconium cyclosilicate; UACR, urine albumin-to-creatinine ratio.

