- Treatment (SZC vs Placebo).
- Geographic region.
- Hyperkalaemia at the beginning of the initiation phase (yes/no), as indicated by the strata applied at randomisation.
- Use of SGLT2i/Finerenone at randomisation (yes/no), as indicated by the concomitant-medications collection.
- Age.

Further covariates may be added as appropriate, and these will be specified in the descriptions below.

Table 2: Overview of the main and the supplementary analyses

|

| Statistical category | Endpoint | Intercurrent event strategy | Population level summary | Details in section |
|--|---|--|--|--------------------|
| Primary | | | | |
| Primary objective #1: To determine if treatment with S2C, as adjunct to ACEi/ARB therapy (lisinopril or valsartan), is superior to placebo in slowing CKD progression, assessed as the reduction in participant's expected eGFR decline over time | | | | |
| Main | Total slope: eGFR measurements starting at randomisation (up to visit 17/week 69) | Main strategy | Difference in mean total eGFR slopes | 4.2.1.1 |
| | Chronic slope: eGFR measurements, starting at 12 weeks after randomisation (up to visit 17/week 69) | Main strategy | Difference in mean chronic eGFR slopes | 4.2.1.1 |
| Supplementary | Total slope: eGFR measurements starting at randomisation (up to visit 17/week 69) | Hypothetical strategy wrt initiation of long-term potassium lowering treatment and initiation of potentially eGFR altering treatment | Difference in mean total eGFR slopes | 4.2.1.2 |
| | Chronic slope: eGFR measurements, starting at 12 weeks after randomisation (up to visit 17/week 69) | Hypothetical strategy wrt initiation of long-term potassium lowering treatment and initiation of potentially eGFR altering treatment | Difference in mean chronic eGFR slopes | 4.2.1.2 |

| Statistical category | Endpoint | Intercurrent event strategy | Population level summary | Details in section |
|----------------------|----------|-----------------------------|--------------------------|--------------------|
| Secondary | | | | |
| | | | | |

Secondary objective #1: To determine if treatment with SZC, as adjunct to ACEi/ARB therapy (lisinopril or valsartan), is superior to placebo in reducing the incidence of the composite of kidney failure outcomes comprising: sustained $\geq 40\%$ decline in eGFR, onset of ESKD, and death from kidney failure

| Statistical category | Endpoint | Intercurrent event strategy | Population level summary | Details in section |

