4.2.1.1 Main analyses

To evaluate the primary objective a linear mixed effects model will be fitted for each of the primary endpoints. It will be based on the eGFR values obtained at the scheduled visits at and after randomisation (total slope) and at and after 12-week visit (chronic slope) respectively as the dependent variable. The following covariates will be included as fixed effects in the model, in addition to the ones specified [above](#):

- Time (continuous) since randomisation (days)
- Time and treatment interaction
- UACR at randomization

If the model as specified above becomes ill-conditioned or encounters issues with convergence due to too few observations in one of the categories, the corresponding fixed effect will be removed from the model.

In addition, two random effects, intercept and slope corresponding to the time since randomisation, will be incorporated, with an underlying assumption of an unstructured covariance matrix between the two. A covariance matrix that assumes independence between the residuals within each participant but allows for a different standard deviation at each visit, will be applied. Because of that dependence on visit, and due to the early close-down of the study and the ensuing unavailability of late eGFR measurements, only measurements taken up to and including visit 17 (week 69) will be included in the mixed-effects model; however, all available data, including the (quite few) late eGFR measurements beyond visit 17 (week 69), will be summarised descriptively and listed.

The null hypothesis of no difference in slope between SZC and placebo will be tested by considering the fixed effect of time and treatment interaction term in the model. The estimates of the mean slopes obtained from the model, as well as the estimate of the difference between the two slopes, together with two-sided 95% confidence intervals, will be presented. For the difference in slope, the corresponding p-value will also be provided.

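### SAP 4.2.1.4 ties the subgroup homogeneity test to the subgroup-by-treatment term, which is not the slope effect; it should name the subgroup-by-treatment-by-time term

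*SAP*

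**What the plan says.** SAP 4.2 (Table 2) gives the population-level summary for the chronic endpoint as "Difference in mean chronic eGFR slopes", with the matching entry for the total slope. In SAP 4.2.1.1 the null hypothesis "will be tested by considering the fixed effect of time and treatment interaction term in the model", and the time covariate is "Time (continuous) since randomisation (days".

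SAP 4.2.1.4 lists 14 subgroup factors and fits two sets of models. For estimates and confidence intervals, the main model "will be fitted to each sub-group separately". For the p-value, a further model adds the subgroup factor and an "interaction between the sub-group factor and each of the three main covariates (treatment, time, and the interaction between the two"). The next sentence assigns the test: "The homogeneity of effect will be tested by applying a likelihood ratio test corresponding to the subgroup-by-treatment interaction term".

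Protocol 9.4.2.1 requires subgroup effect estimates for the two potassium cohorts, with a p-value for the matching interaction. It does not say which term that is and leaves the details to the SAP.

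**The concern.** The subgroup model holds two different interactions between subgroup and treatment: one on eGFR level (subgroup by treatment) and one on slope (subgroup by treatment by time). The SAP has just listed treatment and treatment-by-time as separate covariates, so the term it names for the test is, word for word, the first. The question being asked is about the second.

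With time counted from randomisation, the two-way term is the subgroup difference in the fitted treatment contrast at day 0. Protocol Table 2, footnote b, says of the randomisation visit: "All assessments/procedures designated at this visit should be performed prior to randomising the subject". All 14 factors are also fixed by then. The true day-0 contrast is therefore zero by design in every subgroup, and under linear decline the named test has nothing to find. In the chronic model day 0 is an extrapolation back from week 12, so the term picks up subgroup differences in the acute effect, which the chronic slope is meant to set aside.

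Three readings are open to a programmer: the two-way term, the three-way term, or both jointly. They give different p-values. For geographic region, with four levels, the joint test would have 3 + 3 = 6 degrees of freedom instead of 3. At stake are 14 × 2 = 28 homogeneity p-values, including the cohort comparison that the protocol requires. A non-significant result from an uninformative test could be reported as evidence of consistency.

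**Working it through.** **Inputs.** From SAP 7.3: random-slope SD 2.6, residual SD 7.7, design slope difference 0.75 per year, 1220 complete participants (610 per arm). From the protocol's schedule: central eGFR at weeks 0, 6, 12, 16, 20, 24, 34, 46, 57 and 69; the chronic model uses the eight visits from week 12. Assumed: random-intercept SD 10, uncorrelated with slope (a uniform spread over the 25–59 eligibility range gives 34/√12 = 9.8); equal subgroups; complete data. N = 600 is shown as well because the achieved number is not in the documents.

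**1. Reproduce the plan's power.** Per-participant slope SD = √(2.6² + 7.7²/Sxx), with Sxx the sum of squares of visit times in years on the 104-week schedule.
- Total: Sxx = 6.709, SD = 3.949, SE = 3.949 × √(2/610) = 0.226, power 91.3% (SAP: 91%).
- Chronic: Sxx = 4.857, SD = 4.355, SE = 0.249, power 85.3% (SAP: about 85%).

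**2. Standard errors of the two subgroup terms, data to week 69.** Each term is a difference of differences over four cells of 305, so variance = 4 × (per-participant variance)/305.
- Slope variance = 2.6² + 7.7²/Sxx. Total: Sxx = 1.700, variance 41.64, SE(three-way) = √(4 × 41.64/305) = 0.739. Chronic: Sxx = 1.101, variance 60.61, SE = 0.892.
- Day-0 variance = 10² + 7.7² × (1/n + t̄²/Sxx). Total: n = 10, t̄ = 0.544 years, variance 116.3, SE(two-way) = 1.235. Chronic: n = 8, t̄ = 0.666, variance 131.3, SE = 1.312.
- N = 600 (150 per cell): 1.054 and 1.271 (three-way), 1.761 and 1.871 (two-way).

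**3. Subgroups differ only in slope effect.** The two-way term has expectation zero, so it rejects at 5% whatever the variances. Rejection rates for assumed differences of 0.75 / 1.5 / 3.0 per year:

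| Test | Total | Chronic |
|---|---|---|
| Two-way (as written) | 5 / 5 / 5% | 5 / 5 / 5% |
| Three-way, N = 1220 | 17 / 53 / 98% | 13 / 39 / 92% |
| Three-way, N = 600 | 11 / 30 / 81% | 9 / 22 / 66% |
| Joint 2 df, N = 1220 | 14 / 46 / 97% | 12 / 36 / 92% |

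A 25/75 split at N = 1220 lowers the three-way figures to 14/42/94% (total) and 11/31/83% (chronic). With four equal regions, one of them differing, the 3-df three-way test has 10/28/85% and 8/20/68%.

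**4. Chronic model; subgroups differ only in acute effect.** If an acute difference d is complete by week 12 and the chronic slope effects are equal, the fitted two-way term has expectation d and the three-way term zero. For assumed d = 2 or 3 mL/min/1.73 m²:
- Two-way: 33% or 63% (N = 600: 19% or 36%).
- Joint: 30% or 60% (N = 600: 17% or 33%).
- Three-way: 5%.

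Over intercept SDs from 15 down to 5, the two-way rates run 19–64% (d = 2) and 37–94% (d = 3) at N = 1220, and 12–37% and 21–69% at N = 600.

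**5. Total-slope model.** No false-signal argument is made here. An acute difference of 3 complete by week 6 or 12 is flagged 42% or 31% of the time by the two-way term and 26% or 44% by the three-way term.

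**6. Simulation with estimated variances.** Likelihood ratio tests under maximum likelihood, 400 replicates, N = 1220. At a slope-effect difference of 3.0 the two-way term rejects 3.5% (total) and 6.2% (chronic), the three-way term 98.8% and 93.5%. With an acute difference of 3 in the chronic model: two-way 67%, three-way 6.8%, joint 65%.

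**The case against.** The strongest reply is that the phrase is shorthand. The section sets out to examine homogeneity of the main-analysis effect, which is a slope difference. The sentence before the disputed one puts the three-way term into the model, and dropping a two-way term while keeping the three-way term would be an unusual comparison. That is a fair reading of intent and may be correct. However, the SAP names interaction terms literally elsewhere (time and treatment in 4.2.1.1, treatment-by-visit in 4.2.5.2), and no sentence names the three-way term. A pre-specified test should not depend on guessing.

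The second reply is that little hangs on it, and much of that stands. The p-values are supportive and lie outside the error-controlled families of SAP 3.3.4. The separately fitted subgroup slopes would still show any heterogeneity. At a subgroup difference equal to the design effect of 0.75, the right test has only 17% or 13% power even at N = 1220. The larger power figures need differences of two to four times that effect.

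Third, the false-signal rates rest on assumed acute differences and an assumed intercept SD. Protocol 4.2.2.1 reports acute effects of RAASi and SZC on eGFR but does not say that they differ between subgroups. The concern is plausible for dose-defined factors such as "SZC dose at randomization (5g QOD or 0, 5, 10, 15 g QD") and RAASi dose at randomisation, but it remains an assumption. The failure to detect slope heterogeneity does not depend on it.

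**Conclusion.** The point holds. Followed as written, SAP 4.2.1.4 tests a day-0 contrast that is zero by design and cannot detect the slope heterogeneity it is meant to examine. That conclusion rests only on linear decline, the time origin at randomisation and the pre-randomisation day-0 sample. The power and false-signal figures also need the assumed intercept SD, equal subgroups and complete data, so they are illustrations and probably optimistic, given that the study closed early. The joint reading loses little power but keeps most of the sensitivity to acute differences. The reach is limited to the 28 supportive homogeneity p-values. It should be fixed, because the remedy is nearly free and does no harm if shorthand was intended.

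**What to change.** Replace the test sentence in SAP 4.2.1.4 with:

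> Homogeneity of effect will be tested with a likelihood ratio test (models fitted by maximum likelihood) of the subgroup-by-treatment-by-time interaction term, with degrees of freedom equal to the number of subgroup levels minus one.

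Maximum likelihood is named because the two models compared differ in a fixed effect. The cost is one SAP sentence and one programming line.

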4.2.2 Analyses of Secondary objective #1

Secondary objective #1: To determine if treatment with SZC, as adjunct to ACEi/ARB therapy (lisinopril or valsartan), is superior to placebo in reducing the incidence of the composite of kidney failure outcomes comprising: sustained $\geq 40\%$ decline in eGFR, onset of ESKD, and death from kidney failure.

4.2.2.1 Main analysis

Derivations:

Time to the first occurrence of the components as listed in Table 2, namely sustained $\geq 40\%$ decline in eGFR, onset of ESKD or death from kidney failure, will be derived as the difference between the date of the occurrence and the randomization date, plus one day.

Explicitly, for the different components as listed in CSP Section 8.1.2:

Sustained percent decline in eGFR, is defined as percent decline in eGFR of $\geq 40\%$ from the point of randomisation over at least 4 weeks, as evidenced by 2 consecutive central

laboratory measurements taken at least 4 weeks apart. The start date of the event is the date of the first central laboratory measurement.

Onset of ESKD, is defined as meeting any of the three of the following conditions:

- Kidney transplantation, the date of which is collected directly in the eCRF in a dedicated renal event module.
- Maintenance dialysis, defined as dialysis performed for at least 4 weeks. The date of the start of the dialysis will be used as onset of ESKD date.
- Sustained low eGFR, defined as eGFR < 15 mL/min/1.73 m² over at least 4 weeks, as confirmed by 2 consecutive, non-missing central laboratory measurements < 15 mL/min/1.73 m² taken at least 4 weeks apart. The date of the first such measurement will be used as the date of onset of ESKD.

Death from kidney failure is defined directly by the investigator in the eCRF, as an AE, with the AE date being considered as the date that the event has occurred.

Analysis:

The evaluation of the secondary objective of reducing the incidence of composite outcome of $\geq 40\%$ sustained decline in eGFR, onset of ESKD, and death from kidney failure, will be performed by means of a Cox regression.

The patients will be censored at the end of the maintenance phase, or at the time they leave the study prematurely for any reason (e.g., the date of ICF withdrawal, or the date of last contact in case of a patient lost to follow-up), if such an event occurs. The null hypothesis of no difference between the treatment arms will be tested by considering the hazard ratio (HR) estimate corresponding to treatment. As for other analyses, the estimates of the treatment effect (i.e., hazard ratio between the two treatment arms) alongside the corresponding 95% CI and a p-value, will also be provided.

